Better penetration of ARVs into the CNS (brain and CSF) is associated with improved neuropsychological performance [8, 9]. Some indirect evidence suggests MVC may achieve therapeutic concentrations in the CNS. In a pilot-study of HIV uninfected women (n=12), MVC 300 mg twice-daily for 7 days achieved exposure levels in cervicovaginal fluid and vaginal tissue comparable or exceeding plasma concentrations [48], suggesting MVC is able to penetrate pharmacokinetic sanctuary sites. In addition, MVC is a substrate for P-glycoprotein (Pgp). Co-administration of ritonavir, a P-gp inhibitor, increased CSF exposure of indinavir by inhibition of P-gp-mediated efflux across the BBB [49, 50]. Potentially, co-administration of a ritonavir-boosted protease-inhibitor (PI/r) will enhance the CNS penetration of MVC.

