4.0 SELECTION AND ENROLLMENT OF SUBJECTS

4.1 Inclusion Criteria (Main Study)

- 4.1.1 HIV-1 infection documented by a rapid HIV test or any licensed ELISA test kit and confirmed by a different method ELISA, Western blot, rapid HIV test, or plasma HIV-1 RNA assay at any time prior to study entry. Alternatively, if a licensed ELISA is not available, two HIV-1 RNA values >2000 copies/mL at least 24 hours apart by any CLIA certified laboratory may be used to document HIV-1 infection at any time prior to study entry.
- 4.1.2 All available CD4+ T cell counts within the last 12 months of screening below 350 cells/ mm^3 (minimum of 3 values obtained ≥ 30 days apart).
- 4.1.3 CD4+ cell count below than 350 cells/ mm^3 determined by site clinical laboratory within 30 days of screening.
- 4.1.4 Subject receiving a stable (for at least 6 months) antiretroviral regimen consisting of at least 2 NRTIs and either a protease inhibitor boosted with low dose ritonavir or an NNRTI. A stable regimen is defined as no additions or deletions for more than 14 cumulative days.
- 4.1.5 Subject considered to be receiving initial HIV regimen (history of medication substitution for toxicity is allowed).
- 4.1.6 All available plasma HIV RNA levels within the last 12 months are below the level of detection. Isolated values that are detectable but < 1000 copies will be allowed as long as the plasma HIV RNA levels before and after this detectable time point are undetectable – The subject should have a minimum of 3 values obtained ≥ 30 days apart.
- 4.1.7 Screening plasma HIV RNA levels below level of detection (< 50 copies RNA/mL using Roche Amplicor or < 75 copies/mL using Bayer bDNA) obtained by site clinical laboratory within 30 days of screening.
- 4.1.8 Greater than 90% adherence to HIV therapy within the preceding 30 days, as determined by self-report.

- 4.1.9 Laboratory values obtained by screening laboratories within 30 days of entry:
- Absolute neutrophil count (ANC) $\geq 750/\text{mm}^3$.
 - Hemoglobin ≥ 8.0 g/dL.
 - Platelet count $\geq 50,000/\text{mm}^3$.
 - Calculated creatinine clearance (CrCl) ≥ 50 mL/min as estimated by the Cockcroft-Gault equation:
 - * For men, $(140 - \text{age in years}) \times (\text{body weight in kg}) \div (\text{serum creatinine in mg/dL} \times 72) = \text{CrCl (mL/min)}$
 - * For women, multiply the result by 0.85 = CrCl (mL/min)
 - AST (SGOT), ALT (SGPT), and alkaline phosphatase $\leq 5 \times \text{ULN}$.

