6.2.6 Change in Background Antiretroviral Regimen

- a. Subjects who change their background treatment regimen before week 4 will be discontinued from the study. Those subjects that change their background treatment regimen after week 4 and who choose to continue MVC treatment intensification will be followed on the study.
- b. If the regimen change is due to toxicity, then the subject would be followed per criteria of a Change of Therapy Due to Toxicity visit (section 6.1).

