9.2.2 Secondary

1. CD4+ T-cell absolute count and percentage at baseline, weeks 4 and 24.
2. The proportion of CD4+/CD8+ T-cell immune activation, maturation, regulatory and apoptosis markers at baseline and weeks 4 and 24.
3. Grades ≥ 2 laboratory abnormalities and signs and symptoms.
4. Paired plasma to CSF ratios of MVC concentration at week 4.
5. Soluble immune activation markers in CSF at baseline and week 4.
6. HIV RNA loads in CSF at baseline and week 4.

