9.4.3.1. Analysis of Secondary Objectives

Secondary analyses will include descriptive statistics and tests of significance between pre- and post-MVC intensification. All significance tests will be two-sided and no adjustment for multiple comparisons will be made. If necessary due to assumption failures, appropriate non-parametric statistical tests will be applied.

1. Differences in the change in CD4+ T-cell absolute count and percentage from baseline to week 4 and baseline to week 24 will be compared descriptively via separate paired Student t-tests. Repeated CD4+ T-cell absolute count measured at different time points (3 historic time-points, baseline, week 4, and week 24) will be treated as the outcome variable in a linear mixed-effects model. The primary fixed effects will include time, period (MVC vs. pre-MVC), and interaction between time and period; random effects will include both intercept and slope allowing each subject to have individual starting CD4+ T-cell counts and rate of change. Baseline covariate adjustment will be included if necessary. A significant interaction term between time and period with positive coefficient will indicate if the rate of CD4 recovery is greater during MVC compared to pre-MVC.

2. Differences in the rate of CD4+ T-cell recovery (absolute count and percentage) during MVC intensification in subjects receiving a PI/r- vs. NNRTI-based regimen will be compared via the linear mixed effects model. The fixed effects will include time, regimen (PI/r vs NNRTI), and regimen-by-time interaction; random effects will include both intercept and slope. The regimen-by-time interaction term in the model will indicate the difference in CD4+ T cell recovery rates between the two regimen groups. Baseline covariate adjustment will be included if necessary.

3. Differences in gene expression profiles between subjects receiving a PI/r vs. NNRTI-based regimen at baseline and weeks 4 and 24 will be examined by comparing the gene lists generated in the primary analysis by regimen type. If necessary, statistical modeling will include a dichotomous variable to indicate regimen type.

4. Differences in the proportion of CD4+/CD8+ T-cell immune activation, maturation, regulatory and apoptosis markers between baseline and weeks 4 and 24 will be compared cross-sectionally via McNemar's test or paired t-tests as appropriate.

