5. Association between change in early immune subsets and phase 2 CD4 recovery will be assessed via Pearson's correlation analysis.

6. MVC plasma to CSF ratios at weeks 4 and 24 will be reported via descriptive statistics. Differences in MVC concentration ratios between subjects receiving a PI/r- vs. NNRTI-based background regimen will be compared via McNemar's test or paired t-tests as appropriate.

7. Descriptive statistics of CNS markers of immune activation will be reported via descriptive statistics. Differences in CNS markers of immune activation between baseline and weeks 4 and 24 will be compared cross-sectionally via McNemar's test or paired t-tests as appropriate.

8. Association between change in CNS markers of immune activation and MVC plasma to CSF ratios will be assessed via Pearson's correlation analysis.

9. Descriptive statistics of toxicity/intolerance during MVC treatment intensification will be reported via descriptive statistics. Differences in proportions of grades > 2 laboratory abnormalities and signs and symptoms will be compared via McNemar's test between time points.

10. Virologic failure during MVC treatment intensification will be reported via descriptive statistics.

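### The PI/r versus NNRTI comparison of MVC plasma-to-CSF ratios is between different people, but only paired tests are named

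*Combined protocol and SAP*

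**What the plan says.** Section 9.4.3.1, item 6, first promises descriptive statistics for the MVC plasma-to-CSF ratios at weeks 4 and 24. It then adds a regimen comparison: "Differences in MVC concentration ratios between subjects receiving a PI/r- vs. NNRTI-based background regimen will be compared via McNemar's test or paired t-tests", followed by the qualifier *as appropriate*.

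The other relevant places are these:

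- **Who is compared.** Criterion 4.1.4 requires at least two NRTIs plus "either a protease inhibitor boosted with low dose ritonavir or an NNRTI".
- **What is measured.** Section 9.2.2, endpoint 4: "Paired plasma to CSF ratios of MVC concentration at week 4".
- **Why it is compared.** Section 2.4 expects that "co-administration of a ritonavir-boosted protease-inhibitor (PI/r) will enhance the CNS penetration of MVC", and hypothesis 1a in 2.4.1 predicts higher CSF levels in subjects on a PI/r.
- **How the same contrast is handled for CD4.** Item 2: "The fixed effects will include time, regimen (PI/r vs NNRTI), and regimen-by-time interaction".
- **Where the same test wording recurs.** Item 7: "Differences in CNS markers of immune activation between baseline and weeks 4 and 24 will be compared cross-sectionally via McNemar's test or paired t-tests". Item 4 uses it for the T-cell markers.
- **General fallback.** The opening paragraph of 9.4.3.1: "If necessary due to assumption failures, appropriate non-parametric statistical tests will be applied".
- **Regimen changes.** Section 6.2.6: "Those subjects that change their background treatment regimen after week 4 and who choose to continue MVC treatment intensification will be followed".

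**The concern.** A paired t-test works on differences within matched pairs. McNemar's test works on matched binary outcomes. Item 6 has neither: the outcome is a continuous ratio, and the subjects on a PI/r are different people from those on an NNRTI.

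Two things can follow. The analyst may form arbitrary pairs across regimens. The p-value then depends on the pairing, degrees of freedom are lost, and subjects are dropped whenever the groups differ in size. Or the analyst may substitute a two-sample test, chosen after the data are in hand and different from the written plan. Item 6 is the only listed test of MVC penetration by background regimen, so the plan has no other specification to fall back on.

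**Working it through.** **1. Is there any pairing across regimens?**

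- Eligibility puts each subject in one class, in a single-arm study that adds MVC to the existing regimen. No matching or crossover is described.
- Plasma and CSF are paired within a subject, but forming the ratio already uses that pairing. One ratio per subject per visit remains.
- Weeks 4 and 24 are paired within a subject, but that is a time contrast and not a regimen contrast.
- A subject who changes class after week 4 could supply a ratio under each class. That would be incidental, and item 6 is worded as a comparison between subjects.

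**2. Does other wording supply an unpaired test?** The qualifier *as appropriate* chooses between two tests that are both paired. The fallback is triggered by assumption failures and names no independent-groups test. Items 4 and 7 use the same test phrase for comparisons with baseline, where it fits, so item 6 looks like carried-over wording. Item 2 treats the same regimen contrast as between-subject.

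**3. Cost of carrying it out literally.** The plan gives no power or precision for this comparison, so there is no figure to reproduce. Inputs: up to 17 participants (section 3.2) and two-sided tests (9.4.3.1). Assumptions: a 5% level, normal data, equal SDs, zero correlation within arbitrary pairs, and the splits shown. Let n1 and n2 be the group sizes and k the smaller of them. In SD units the 95% half-widths are:

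- paired: t(0.975; k−1) × √(2/k)
- two-sample: t(0.975; n1+n2−2) × √(1/n1 + 1/n2)

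For 9/8, paired is 2.365 × √(2/8) = 1.182. Two-sample is 2.131 × √(1/9 + 1/8) = 1.036. The ratio is 1.182/1.036 = 1.14. Power is from the noncentral t at a true difference of 1 SD.

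| Split | Dropped | Half-width, paired | Half-width, two-sample | Widening | Power, paired | Power, two-sample |
|---|---|---|---|---|---|---|
| 8/8 | 0 | 1.182 | 1.072 | 10% | 41% | 46% |
| 9/8 | 1 | 1.182 | 1.036 | 14% | 41% | 49% |
| 10/7 | 3 | 1.308 | 1.050 | 25% | 35% | 48% |
| 11/6 | 5 | 1.484 | 1.082 | 37% | 29% | 45% |
| 12/5 | 7 | 1.756 | 1.135 | 55% | 23% | 42% |

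With smaller equal groups the widening is 12% for 7/7 (1.308 v 1.165) and 15% for 6/6 (1.484 v 1.286).

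**4. How much does the p-value depend on the pairing?** This was simulated with 8 v 8 normal observations, 10,000 datasets and 200 random matchings of each. A dataset counts as unstable if the 5th and 95th percentiles of its p-values fall on opposite sides of 0.05.

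| True difference (SD) | 0 | 0.5 | 1 | 1.5 | 2 |
|---|---|---|---|---|---|
| Unstable datasets | 14% | 27% | 46% | 40% | 16% |

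Average rejection at no difference was 5.0%. A matching fixed without regard to results therefore keeps the type I error; the loss is in precision and reproducibility.

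**5. Separate check: the lumbar puncture count in 3.2.** The stated figure of about 43 punctures in people taking MVC matches 17 × 2.5 = 42.5. One of the three planned punctures is before treatment and yields no MVC ratio. At most 17 × 2 = 34 can be on drug. If every participant has the baseline puncture and the average is 2.5, the number is 17 × 1.5 = 25.5, about 26.

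**The case against.** The best case for leaving this alone is that it is a wording slip with an obvious correction, in one of ten unadjusted secondary analyses of a pilot. Software will not run a paired test on groups of unequal size, so a competent analyst would use a two-sample test and the losses tabulated above would never occur. The absence of pairs could itself be called an assumption failure, which would open the way to a rank-sum test under the fallback clause. The descriptive reporting of ratios in item 6 is unaffected either way.

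Much of this stands. The widening and instability figures describe literal execution and are not a forecast. The realistic harm is an undocumented departure from the plan. The fallback argument is only partial, since the non-parametric counterpart of a paired t-test is also a paired test, and no unpaired test is named anywhere for this item.

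It is also fair to say that a timing covariate and a restriction on raw CSF comparisons go beyond correcting the test. They are optional. The puncture count is a separate matter: its derivation as 17 × 2.5 is inferred (60% of 30 would be 18 participants and 45 punctures), and no stated power depends on it. It adds nothing to the weight of this point.

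**Conclusion.** The concern holds. Item 6 names only paired tests for a contrast between independent groups, which conflicts with criterion 4.1.4 and with the plan's own handling of the same contrast in item 2. This conclusion needs no numerical assumption.

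The consequence is small. If done literally with all 17 subjects, the interval is 14% to 55% wider across splits from 9/8 to 12/5, and power at 1 SD falls by about 8 to 19 percentage points (48.6% to 40.8% for 9/8; 42.0% to 23.1% for 12/5). Those sizes rest on the assumed splits, effect size, normality and equal SDs. Type I error stays near 5%, and the primary gene-expression analysis is untouched. It should be fixed because the wording is wrong and the correction is nearly free. The ratio itself is a reasonable measure of CNS penetration and is not in dispute.

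**What to change.** **Necessary.** In item 6, replace the two paired tests with an independent-groups comparison at week 4: a two-sample t-test on log ratios, or a Wilcoxon rank-sum test. If weeks 4 and 24 are analysed together, use a mixed model with regimen as a between-subject factor and a random subject effect, in line with item 2, and state which regimen counts for a subject who switches after week 4.

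**Advisable.** Report post-dose sampling time by regimen, because section 3.2 varies it on purpose. Keep any comparison of raw CSF concentrations by regimen descriptive, noting that MVC dose differs with background regimen (5.1) and that sampling time varies.

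**Optional.** Add post-dose interval as a covariate. With a 9/8 split the minimum cost is one degree of freedom, 2.145/2.131, or about 0.6% on the half-width. That holds only if timing is exactly balanced across regimens. With a two-level interval assigned at random, the median widening is about 2% and the 95th percentile about 18%.

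**Separate correction in 3.2.** Restate the yield as about 43 lumbar punctures in total, of which at most 34 can be on MVC (about 26 if every participant has the baseline puncture).

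The cost is a change of wording in item 6 and one restated planning figure. Visits, samples and sample size do not change.

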2.4.1 Hypotheses

1. Maraviroc (MVC) concentrations in CSF will approximate 24% of the plasma C_{min} and will vary across the dosing interval.
 - a. Subjects receiving background HIV therapy containing a PI/r will achieve higher CSF MVC concentrations than those receiving not receiving a PI/r
2. MVC treatment-intensification will decrease immune activation (activated T-cells and pro-inflammatory cytokines) in the CSF.
3. Among subjects with CSF viral replication above 2 copies/mL at baseline, all will be suppressed below 2 copies/mL after 4 weeks of MVC treatment-intensification.

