3.2 Study Design (CSF Sub-Study)

This is a sub-study of the MVC treatment-intensification protocol (i.e., a “piggyback” protocol). The primary eligibility criteria will be enrollment into the MVC parent study, ability to give informed consent to lumbar puncture (LPs), and the absence of medications or conditions that would contraindicate lumbar puncture (e.g., coagulopathy). Pre-treatment LPs will be performed, followed by a LP at week 4 of MVC treatment intensification (i.e., “steady state”). All LPs will be performed within one hour of a parent protocol-dictated blood draw, reducing the need for separate visits or additional phlebotomy. For subjects willing to undergo more than one LP, an additional LP will be performed at week 24 of MVC treatment intensification. The primary study outcomes will be measurement of MVC concentrations and reductions in markers of immune activation levels in CSF at week 4.

The study will aim to obtain 3 LPs in as many subjects as possible with the goal being at least two LPs separated by at least 4 weeks in up to 17 participants. After informed consent is obtained, subjects will undergo a brief screening to ensure the absence of contraindications to LP. If eligible subjects choose to enroll, subsequent visits will occur at major visits of the parent protocol (baseline, week 4 and 24). Based on prior experience we conservatively estimate that approximately 60% of subjects in the parent protocol will be willing to consent to lumbar puncture an average of 2.5 LPs per consenting subject. In total, we estimate that this CSF sub-study will yield approximately 43 LPs from individuals taking MVC. Post-dose timing of the lumbar punctures will be limited by the parent protocols but we will strive to vary the post-dose lumbar puncture interval in order to have approximately equal representation from two intervals.

- Interval 1: 2 - 6 hours post dose
- Interval 2: 6 - 12 hours post dose

If successful, this variation across the dosing interval will improve the accuracy of population pharmacokinetic modeling.

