3.6 Lumbar Puncture

Standard lumbar puncture-related adverse events will be monitored following all visits. Lumbar punctures will be performed under aseptic conditions at the clinical facilities of the HNRC by a neurologist, an internist, or by a trained registered nurse working under the supervision of the neurologist. Standard risks associated with HNRC medical procedures include 1) venipuncture: the risk of pain, bruising, and a very low risk infection; and 2) lumbar puncture: the risk of pain, bruising and a very low risk of infection as well as a risk of post-dural puncture cephalgia which can range from mild to severe.

Routine clinical lab assays (cell counts, glucose, total protein) will be performed on all CSF. HIV RNA will be measured with a modified version of the Biomerieux assay validated to quantify HIV as low as 2 copies/mL in CSF [51]. MVC concentrations will be measured in plasma and CSF. Remaining specimens will be aliquoted and then stored at -70C at the HIV Neurobehavioral Research Center (HNRC) Specimen Bank.

Local back pain will be minimized by injection of an anesthetic, 1% lidocaine into the subcutaneous tissue surrounding the needle puncture site. Oral analgesics and anti-inflammatory medications will be provided when necessary. Following LP, patients will be observed for 10-15 minutes. Over 3,000 LPs have been performed at the HNRC using non-cutting or "pencil point" spinal needles that reduce the risk of post-LP cephalgia. A site clinician will be available by pager 24 hours-per-day to respond to problems, should they occur. If post-LP headache occurs, initial conservative management will include recumbency, hydration, and oral analgesics. When headaches are prolonged, a blood patch, involving an epidural injection of a sample of the subject's own blood, may be performed by consulting anesthesiologists. This is extremely effective in aborting post-LP headache, but is only necessary in fewer than 1% of HNRC subjects. Palliative procedures will be performed at no cost to the participant.

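### The CSF sub-study's only drug-level-to-response analysis uses the plasma-to-CSF ratio, in which shared systemic exposure cancels; measured CSF maraviroc concentration is not used as an exposure in any analysis

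*Combined protocol and SAP*

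**What the plan says.** Item 8 of section 9.4.3.1 reads: "Association between change in CNS markers of immune activation and MVC plasma to CSF ratios will be assessed via Pearson's correlation analysis". It does not say which visit's ratio or which change is meant, and it has no term for time after dose.

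The CSF level itself is available. Section 3.6 says that "MVC concentrations will be measured in plasma and CSF". Section 3.2 describes the sub-study's outcomes as follows: "The primary study outcomes will be measurement of MVC concentrations and reductions in markers of immune activation levels in CSF at week 4". Hypothesis 1a in section 2.4.1 is also worded in terms of CSF level: "Subjects receiving background HIV therapy containing a PI/r will achieve higher CSF MVC concentrations". The endpoint list in section 9.2.2, however, names "Paired plasma to CSF ratios of MVC concentration at week 4", and both items of section 9.4.3.1 that use a drug level (6 and 8) use the ratio.

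On timing, section 3.2 says "we will strive to vary the post-dose lumbar puncture interval in order to have approximately equal representation from two intervals", the two being "Interval 1: 2 - 6 hours post dose" and "Interval 2: 6 - 12 hours post dose". Each LP is to fall within an hour of a blood draw. Population PK modelling is mentioned there but is not linked to item 8.

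**The concern.** The rationale in sections 2.3 and 2.4 is receptor antagonism that reduces immune activation, in the CNS through macrophages and microglia. For that mechanism the relevant exposure is the amount of drug at the site. A plasma-to-CSF ratio instead says how freely the drug crosses. Two subjects whose CSF levels differ fourfold have the same ratio if their plasma levels also differ fourfold.

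Item 8 is the only planned analysis that links any MVC level to a response. As written, it can show whether penetration tracks the change in markers, but not whether CSF exposure does. A null result would say little about CSF exposure. The direction is also easy to misread, because a larger plasma-to-CSF value means poorer penetration.

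The unadjusted draw time is a second, smaller problem. Whatever part of the plasma time course CSF does not follow enters the ratio as noise.

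**Working it through.** **Plan's own figures.** No power or effect size is given for item 8. The only sub-study size figure is the LP yield in section 3.2: 17 subjects x 2.5 LPs = 42.5, about 43, which reproduces. The n for a per-visit correlation is at most 17.

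**What n = 17 can detect.** Fisher z, two-sided 5% (assumed; the plan says two-sided but gives no level for secondary tests): power = Phi(atanh|r| x sqrt(14) - 1.96). For |r| = 0.4, 0.5, 0.6 and 0.7 this gives 35%, 54%, 74% and 90%. For 80% power, |r| = tanh((1.96 + 0.84)/sqrt(14)) = 0.63.

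**What the ratio does, with no timing effect.** Let a be a subject's log plasma level (SD s_a) and b the log penetration (SD s_b), independent. Then log CSF = a + b and log(plasma/CSF) = a - (a + b) = -b, so a has gone. If marker change has correlation -0.6 with log CSF, and depends on a and b only through it, its correlation with the log ratio is 0.6 x s_b / sqrt(s_a^2 + s_b^2). The SDs are assumptions.

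| s_a / s_b | correlation with log ratio | power, Fisher z | power, simulated, no timing effect |
|---|---|---|---|
| 0.5 / 0.3 | 0.6 x 0.3/0.583 = 0.31 | 22% | 23% |
| 0.4 / 0.4 | 0.6 x 0.4/0.566 = 0.42 | 40% | 41% |
| 0.3 / 0.5 | 0.6 x 0.5/0.583 = 0.51 | 57% | 59% |

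The comparator, log CSF itself, has 74% by the same formula. Cancellation alone therefore accounts for most of the loss.

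**Adding draw time.** Simulation, 20,000 replicates per cell, n = 17, LP time uniform over 2-12 h, no assay error. Plasma falls not at all, or 2-, 5- or 10-fold over that span. CSF follows none, half or all of the fall. The marker is driven by the subject's time-independent CSF level. All of these are assumptions.

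| s_a / s_b | ratio, unadjusted | ratio, time-adjusted | log CSF, unadjusted | log CSF, time-adjusted |
|---|---|---|---|---|
| 0.5 / 0.3 | 8-23% | 21-22% | 34-77% | 73-74% |
| 0.4 / 0.4 | 13-41% | 38-39% | 34-76% | 73-74% |
| 0.3 / 0.5 | 22-59% | 56-57% | 36-77% | 73-74% |
| 0 / 0.5 (penetration only) | 30-76% | 73-74% | 29-77% | 73-74% |

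Two features matter. Adjusting the ratio for time does not recover the loss when plasma level varies between subjects. And unadjusted log CSF is not safe: with a 10-fold plasma fall that CSF follows fully, it has 34-36% in the first three rows, against 23%, 41% and 59% for the ratio.

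**Sensitivity.** A second model used untransformed values, assay error (log-SD 0.15) and half the draws in each interval. The ratio had 8-13% power against 43-67% for unadjusted CSF concentration when plasma level dominates (0.6 / 0.3), and 31-51% against 43-67% when penetration dominates (0.3 / 0.6).

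**The case against.** The ratio is a declared endpoint (section 9.2.2), objective 1.2.5 compares CSF with plasma, and section 2.4 is largely about penetration. Asking whether penetration relates to response is legitimate, and section 2.4.1 states no exposure-response hypothesis. This stands: the ratio should be kept and supplemented, not discarded.

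Plasma and CSF are paired within an hour, so when CSF tracks plasma the ratio removes timing while a single CSF concentration retains it. Section 2.4.1 expects CSF levels to vary over the dosing interval. This also stands. It rules out an unadjusted CSF correlation as the remedy, and it means that a simulation with flat CSF alone would overstate the gain.

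A reader might infer that a true CNS exposure-response would largely be missed whatever the circumstances, or that sampling time is the main culprit. The documents support neither. The loss depends on how much of the CSF variation comes from plasma level, for which no variances are given, and it is present with no timing effect at all. A reader might also expect a null item 8 to be reported as showing that CNS exposure does not matter; nothing in the plan says so.

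Finally, item 8 is one unadjusted secondary correlation in a pilot study with up to 17 subjects. That limits the weight of the point, but not its correctness.

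**Conclusion.** The point holds in conditional form. Item 8 uses a penetration measure in which shared systemic exposure cancels, and no analysis uses the measured CSF concentration as the exposure. Unadjusted draw time over 2-12 h is a secondary source of noise.

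If plasma level contributes materially to between-subject CSF variation, power for a true correlation of -0.6 at n = 17 is about 7-60% with the ratio against 73-74% with time-adjusted log CSF concentration. That condition is plausible, given three dose groups and inhibiting, neutral or inducing background drugs (section 5.1.1), but the documents do not establish it. If only penetration varies, the two measures are equivalent once timing is handled. The SDs, time courses and 5% level are assumed.

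Even the better measure reaches 80% power only for |r| of about 0.63, so the analysis stays exploratory. The main study's primary endpoint is untouched. The change is worth making because it is nearly free.

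**What to change.** In item 8, regress change in each CNS marker on log CSF MVC concentration at the same visit, with time since last dose as a covariate, and name the visit. Do not substitute an unadjusted correlation with CSF concentration. Keep the ratio as the penetration measure in item 6 and as a secondary correlate in item 8, and state which direction of the ratio means better penetration.

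The cost is a sentence or two in the plan, one degree of freedom and one additional exploratory analysis. No new samples or assays are needed. Time since last dose has to be known at each on-treatment LP, which the interval scheme in section 3.2 already implies.
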